### 4.1.1 Inclusion Criteria

Each patient must meet all of the following criteria to be enrolled in this study:

1. Has informed consent form (ICF) signed according to local rules and approved regulations.
2. Is aged 18 to 85 years, inclusive.
3. Is admitted to the ICU or intermediate care unit.
4. Has diagnosis of sepsis (<96 hours prior to first study drug administration or < 72 hours prior to AKI diagnosis), according to criteria defined by the American College of Chest Physicians/Society of Critical Care Medicine (Bone 1992)], based on:
  - a. Has a proven or strongly suspected bacterial infection and
  - b. Have at least 2 of the following 4 SIRS criteria within a timeframe of 72 hours at time of AKI diagnosis. Note: it is not required that symptoms are present simultaneously at study randomization:
    - i. Has a core temperature > 38°C or < 36°C.
    - ii. Has a heart rate > 90 beats/minute (unless the patient has a medical condition known to increase heart rate or is receiving treatment to prevent tachycardia).
    - iii. Has a respiratory rate > 20 breaths/minute, PaCO2 < 32 mm Hg or the use of mechanical ventilation for an acute respiratory process.
    - iv. Has a white cell count > 12 000/mm^3 or < 4000/mm^3 or a differential count showing > 10% immature neutrophils (band cells).
5. Has first diagnosis of AKI, defined as any of the following:

AKI Stage 1 or greater, according to the following Acute Kidney Injury Network (AKIN) criteria (Note: adjusted in regards to time-window):

- a. Increase (absolute) in serum creatinine > 26.2 µmol/L (0.30 mg/dL) compared with a serum creatinine value within the previous 48 hours, or presumed to have occurred in the previous 48 hours when compared to a reference\* creatinine value

- b. Increase (relative) in serum creatinine to  $> 150\%$  ( $> 1.5$ -fold) compared with a serum creatinine value in the previous 48 hours or presumed to have occurred in the previous 48 hours when compared to a reference\* creatinine value.

\*The reference creatinine value is a serum creatinine value in the following order of preference:

1. Lowest value within 3 months of the hospital admission. If not available:
  2. At hospital admission. If not available:
  3. At ICU or intermediate care unit admission. If not available:
  4. Lowest value between 3 and 12 months prior to hospital admission

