### **6.3.6 12-Lead Electrocardiogram**

A 12-lead ECG will be performed at baseline, Day 3, and Day 14 (see Section 13.1 [Table 13-1] and Section 13.2 [Figure 13-1]).

A 12-lead ECG with at least a 30-second rhythm strip will be recorded after the patient has rested supine or semi-recumbent for at least 5 minutes. The recording should be printed, signed, and dated by the investigator (or designee) and retained as source documentation. The ECG print should include the date and time of the assessment and the patient's study number. The interpretation of the investigator or designee will be recorded in the source documents.

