### **6.3.8.3 Pharmacokinetic Assessments**

Pharmacokinetic assessments will be performed during Part 1 only.

The following PK samples will be taken from Day 1 to Day 7 (inclusive) in the first 120 patients from Part 1 only and exact sampling clock times will be recorded:

- Day 1: One pre-dose sample and one post-dose sample near peak (approximately  $2.5 \pm 1.0$  hour after dosing).
- Day 2: One sample near trough ( $1.5 \pm 1$  hour before the second dose) and one sample near peak (approximately  $2.5 \pm 1.0$  hour after Day 2 dosing).\*
- Day 3: One sample near trough ( $1.5 \pm 1$  hour before the third dose) and one sample near peak (approximately  $2.5 \pm 1.0$  hour after Day 3 dosing).\*
- Day 4: One PK sample, random time.
- Day 5: One PK sample, random time.
- Day 6: One PK sample, random time.
- Day 7: One PK sample, random time.

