### **7.7.3 Safety Analyses**

The safety summaries will include all 4 treatment groups, comprising all patients in the safety set.

Treatment-emergent adverse events will be tabulated by treatment group. The number and percentage of patients with at least 1 TEAE will be presented along with a breakdown by system organ class and preferred term, with each patient being counted once at each summarization level. This summary will be repeated for treatment-related TEAEs, TEAEs that lead to study drug discontinuation, by relationship to study drug, by intensity, and for treatment-emergent SAEs.

Laboratory test results (for hematology, clinical chemistry, and urinalysis parameters not considered in the efficacy analyses), vital signs data, and ECG data will be presented in tables summarizing absolute values and change from baseline by treatment group, with shift tables included as appropriate. Other safety data will be listed only.

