9.5. Electrocardiogram

All patients will have a 12-lead ECG performed at baseline, Day 3, and Day 14.

Summary tables presenting observed values and changes from baseline will be presented for ventricular rate (bpm), PR Interval (msec), QRS Duration (msec), QT Interval (msec), QTcB Interval (msec), by treatment group for patients in the Safety Set. Changes from baseline to each scheduled post-baseline visit will be presented.

The ECG interpretations will be summarized in shift tables comparing the ECG values of each post-baseline visit with the value at the baseline visit for the Safety Set. The percentage will be based on the number of patients who have attended the visit. In addition the worst post-baseline ECG value will be compared with the value at the baseline visit (with worst of all being Abnormal and best being Normal).

Electrocardiogram data for all patients will be presented in a listing.

10. Pharmacokinetics and Pharmacodynamics

The pharmacokinetics and pharmacodynamics analyses will be described in the Population Pharmacokinetics/ Pharmacodynamics Report Analysis Plan.

11. Interim Analysis

An unblinded interim analysis will be conducted on the Part 1 data to determine the optimal recAP dose for Part 2. This analysis will compare the 4 treatment groups from Part 1 on the primary efficacy endpoint, and a selection of the safety data. The interim analysis will be conducted when the first 7 days of laboratory data have been collected for 120 patients from Part 1, unless the patient was randomized but died or discontinued prior to completing 7 days.

To maintain the blind, the interim analysis will be conducted and delivered by an unblinded PPD Biostatistics team located at a different site to the blinded PPD biostatistics personnel involved in the study. The results will be reviewed by an independent DMC, who will make the dose selection decision. A futility analysis will also be conducted at the interim analysis. If none of the 3 recAP doses in Part 1 show evidence of efficacy (i.e., all 3 groups have 1-sided, unadjusted p-value greater than 0.8), then the study will be terminated.

The following outputs will be produced for the Interim Analysis:

Table 14.1.1.1.1	Disposition at Interim Analysis All Enrolled Set
Table 14.1.1.6.1	Concomitant Medications at Interim Analysis Safety Set
Table 14.2.1.1.1	Summary of Time-Corrected Endogenous Creatinine Clearance at Interim Analysis ITT Combined Set

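### QTcB is the only corrected QT in the ECG tables, so its within-arm change from baseline is biased downward if heart rate falls; adding QTcF is a minor, nearly free improvement

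*SAP*

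**What the plan says.** SAP 9.5 plans Safety Set tables by treatment group for "ventricular rate (bpm), PR Interval (msec), QRS Duration (msec), QT Interval (msec), QTcB Interval (msec"). It adds that "Changes from baseline to each scheduled post-baseline visit will be presented". The ECGs are those of Protocol 6.3.6: "A 12-lead ECG will be performed at baseline, Day 3, and Day 14". The same SAP section plans shift tables of the normal/abnormal interpretation and a patient listing of ECG data.

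The protocol does not choose a correction. Section 7.7.3 says only that "ECG data will be presented in tables summarizing absolute values and change from baseline by treatment group". No other correction formula appears in either document.

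On heart rate at entry, Protocol 4.1.1 (criterion 4b) lists four SIRS items, one of which is "Has a heart rate > 90 beats/minute". Any two of the four suffice within a 72-hour frame, the heart-rate item carries exemptions, and a note says the signs need not all be present together at randomisation. SAP 6.2 plans to describe baseline heart rate, but neither document gives an expected value or an expected fall.

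**The concern.** Bazett scales QT by the square root of heart rate and Fridericia by the cube root. Above 60 bpm Bazett therefore returns the larger value, and the gap widens as the rate rises. If patients are tachycardic at the baseline ECG and slower on Day 3 or Day 14, QTcB falls even when Fridericia-corrected repolarisation is unchanged. A planned change from baseline that mixes rate with repolarisation can hide a real lengthening within an arm.

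This matters somewhat more here than in a stable population. Tachycardia is one route to meeting the sepsis definition, and Protocol 7.3.2 takes vasopressor and inotrope withdrawal as an endpoint, so a heart-rate fall after baseline is plausible. If recAP itself changed heart rate, the artefact would also enter the comparison with placebo.

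**Working it through.** **Inputs.** From the documents: QTcB is the only correction, QT and ventricular rate are both recorded, and ECGs are taken at baseline, Day 3 and Day 14. The documents give no QT, QTc or heart-rate value, so there is no plan figure to reproduce. Every numerical input below is an assumption: QTcF 400 to 440 ms (420 ms in the tables), and heart rate 95 to 120 bpm falling to 80 to 90 bpm.

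**Formulas** (QT in ms, HR in bpm):
- QTcB = QT × (HR/60)^(1/2)
- QTcF = QT × (HR/60)^(1/3)
- hence QTcB = QTcF × (HR/60)^(1/6)

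**Within-arm change, QTcF held at 420 ms**

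| HR, bpm | Raw QT, ms | QTcB, ms | Change in QTcB, ms |
|---|---|---|---|
| 95 to 90 | 360 to 367 | 453.43 to 449.36 | -4.1 |
| 100 to 90 | 354 to 367 | 457.32 to 449.36 | -8.0 |
| 110 to 90 | 343 to 367 | 464.65 to 449.36 | -15.3 |
| 100 to 80 | 354 to 382 | 457.32 to 440.63 | -16.7 |
| 110 to 80 | 343 to 382 | 464.65 to 440.63 | -24.0 |
| 120 to 80 | 333 to 382 | 471.43 to 440.63 | -30.8 |

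The change in QTcF is 0 in every row by construction. At QTcF 416 ms the 100-to-90 and 120-to-80 rows become -7.9 and -30.5 ms. Across QTcF 400 to 440 ms they run from -7.6 to -8.3 and from -29.3 to -32.3 ms.

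In these rows raw QT lengthens as the rate slows. With raw QT fixed at 340 ms instead, the fall in QTcB is larger: 340 × [(90/60)^(1/2) - (100/60)^(1/2)] = -22.5 ms for 100 to 90 bpm, and -88.2 ms for 120 to 80 bpm.

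**Between-arm bias at a post-baseline visit, QTcF equal at 420 ms in both arms**

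| Placebo HR, bpm | recAP 2 bpm lower | 5 bpm lower | 10 bpm lower |
|---|---|---|---|
| 80 | -1.9 ms | -4.7 ms | -9.7 ms |
| 85 | -1.8 ms | -4.5 ms | -9.2 ms |
| 90 | -1.7 ms | -4.3 ms | -8.7 ms |

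If heart rate is the same in both arms the bias is 0.

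**A real effect seen both ways.** Suppose recAP raises QTcF from 416 to 426 ms while heart rate falls from 110 to 85 bpm in both arms.
- Within the recAP arm: QTcB goes from 416 × (110/60)^(1/6) = 460.22 to 426 × (85/60)^(1/6) = 451.46, a change of -8.8 ms. The increase appears as a shortening.
- Against placebo at 85 bpm: placebo QTcB is 416 × (85/60)^(1/6) = 440.86, so the difference is 451.46 - 440.86 = 10.6 ms. The increase is visible.

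**The case against.** The strongest reply is that the trial has a concurrent randomised placebo arm and that safety results are shown for all four groups. A heart-rate fall common to the arms cancels, as the last example shows. Ventricular rate and uncorrected QT sit beside QTcB in the same tables, SAP 9.3 adds heart rate by arm and visit, and ECG data are listed by patient. This stands for the between-arm contrast unless recAP alters heart rate, which the documents do not claim. It does not repair the within-arm change that SAP 9.5 says it will present. Nor can mean QTcF be recovered from mean QT and mean rate, because the correction is non-linear and applies patient by patient. A hand derivation from the listing would mean choosing a formula after the results are known.

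It is also fair that the illustration treats QTcF as the reference. Fridericia is assumed adequate here, not shown to be so from trial data.

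Four stronger readings are tempting, and the documents do not support them:
- *QTcB falls by 8 to 31 ms with QT itself unchanged.* Those figures hold QTcF constant; raw QT rises in each case.
- *Patients are selected for tachycardia.* The heart-rate item is one of four, two are needed, it has exemptions, and it need not be present at randomisation.
- *A drug effect would be masked against placebo.* That requires heart rate to differ between arms.
- *The Day 3 ECG should be tied to the near-peak sampling window.* That window (Protocol 6.3.8.3) belongs to PK sampling in the first 120 Part 1 patients only. No loss from the present timing can be quantified from the documents, so no timing change is proposed.

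**Conclusion.** The point holds as a minor one. QTcB is the only corrected QT planned, and its within-arm change from baseline is biased downward whenever heart rate falls. Under the assumed values the bias is about 4 ms for a small fall (95 to 90 bpm), 8 ms for 100 to 90 bpm, and 31 ms for 120 to 80 bpm. Between arms it is zero if heart rates match and about 4 to 5 ms for each 5 bpm difference.

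These sizes depend on the assumed heart rates, on QTcF of about 416 to 420 ms, and on Fridericia being the better correction. A reader might infer that the trial's QT safety conclusion is unreliable. That goes too far: the placebo comparison, raw QT and ventricular rate remain available. QTcB feeds no efficacy endpoint, and the interim and DMC outputs listed in SAP 11 include no ECG table.

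**What to change.** In SAP 9.5, derive QTcF = QT × (ventricular rate/60)^(1/3) for each patient and each ECG from the values already recorded. Present it as the main QTc summary (observed value and change from baseline, by visit and treatment group), and keep QTcB as secondary. Specify this before unblinding so that the formula is not chosen on the results.

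The cost is one derived variable and its row in the existing tables and listing. It needs no new data and no change to the ECG schedule.

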15.1. Schedule of Study Procedures

Table 15-1 Schedule of Assessments

Assessment	Screening (≤ 24 h)	Baseline (≤ 24 h)	Day 1	Day 2	Day 3	Day 4	Day 5	Day 6	Day 7 (± 1 day)	Day 14 (± 2 days)	Day 21 (± 3 days)	Day 28 (± 3 days)	Day 60 (± 5 days)	Day 90 (± 10 days)
AKI diagnosis ^a (pre-screening) Record site of infection and pathogen	X													
Inclusion and exclusion criteria	X	X ^b												
Informed consent	X													
Medical history	X													
Demographics	X													
Child-Pugh score ^c	X													
Recent hematology and clinical chemistry results, if available	X													
Recent microbial test results, if available	X													
Pregnancy test (urine or blood) ^d	X													

Assessment	Screening (≤ 24 h)	Baseline (≤ 24 h)	Day 1	Day 2	Day 3	Day 4	Day 5	Day 6	Day 7 (± 1 day)	Day 14 (± 2 days)	Day 21 (± 3 days)	Day 28 (± 3 days)	Day 60 (± 5 days)	Day 90 (± 10 days)
Local laboratory confirmatory serum creatinine sample ^e , or confirmatory assessment of continuation of decreased urine output	X													
Randomization ^f		X												
Vital signs (BP, HR, OS, RR, T) ^g		X	X ^h	X ^h	X ^h	X	X	X	X	X	X	X		
Physical examination		X	X	X	X	X	X	X	X	X	X	X		
APACHE II score		X												
SAPS-2 score		X												
SOFA score ⁱ		X	X	X	X	X	X	X	X	X	X	X		
EQ-5D ^{Error! Reference source not found.}		X												X
Alkaline phosphatase		X												
Time from first diagnosis of SA-AKI to start of recAP treatment		X												
Treatment			X	X ^k	X ^k									

Assessment	Screening (≤ 24 h)	Baseline (≤ 24 h)	Day 1	Day 2	Day 3	Day 4	Day 5	Day 6	Day 7 (± 1 day)	Day 14 (± 2 days)	Day 21 (± 3 days)	Day 28 (± 3 days)	Day 60 (± 5 days)	Day 90 (± 10 days)
Arterial partial pressure of O ₂ (in ICU or intermediate care unit only) for mechanically ventilated patients		X	X	X	X	X	X	X	X	X	X	X		
Blood: serum creatinine and BUN ^l		X ^e	X	X	X	X	X	X	X	X	X	X	X	X
Urine (6 ± 1 h collection) creatinine, BUN ^m		X ⁿ	X	X	X	X	X	X	X	X	X	X		
Volume of urine ^o		X ^p	X	X	X	X	X	X	X	X	X	X		
Pharmacokinetics ^q			X	X	X	X	X	X	X					
ECG (12-lead) ^r		X			X					X				
Hematology (Hgb, Hct, leukocytes, diff leukocytes, erythrocytes, thrombocytes, and APTT) ^d		X	X		X		X		X	X	X	X		
Clinical chemistry (CRP, ALT, AST, GGT, urea, LDH, creatinine, bilirubin, CPK, total protein, albumin, glucose, sodium, potassium, chloride, bicarbonate, and lactate) ^d		X	X		X		X		X	X	X	X		

Assessment	Screening (≤ 24 h)	Baseline (≤ 24 h)	Day 1	Day 2	Day 3	Day 4	Day 5	Day 6	Day 7 (± 1 day)	Day 14 (± 2 days)	Day 21 (± 3 days)	Day 28 (± 3 days)	Day 60 (± 5 days)	Day 90 (± 10 days)
Biomarkers for systemic inflammation (e.g., IL-6, CRP, LBP) ^s		X	X	X	X	X	X	X	X	X	X	X		
Serology (IgG, IgE, and total immunoglobulin) ^s		X								X		X		
Anti-drug antibodies		X								X		X	X ^t	X ^t
Tubular injury biomarkers (e.g., KIM-1, IL-18, GST-alpha) in urine ^s		X	X	X	X	X	X	X	X	X	X	X		
Kidney function markers (urine creatinine, BUN/urea clearance, fractional excretion of urea and urine output) ^s		X	X	X	X	X	X	X	X	X	X	X		
Kidney function markers (sodium and fractional excretion of sodium) ^s		X	X	X	X	X	X	X	X					
Kidney function markers (serum creatinine and proteinuria) ^s		X	X	X	X	X	X	X	X	X	X	X	X	X
Concomitant medication	X ^u	X	X	X	X	X	X	X	X	X	X	X		
Patient on RRT, and start or stop date			X	X	X	X	X	X	X	X	X	X		

Assessment	Screening (≤ 24 h)	Baseline (≤ 24 h)	Day 1	Day 2	Day 3	Day 4	Day 5	Day 6	Day 7 (± 1 day)	Day 14 (± 2 days)	Day 21 (± 3 days)	Day 28 (± 3 days)	Day 60 (± 5 days)	Day 90 (± 10 days)
Need for dialysis dependency													X	X
Name, start or stop date, and dose of vasopressor and inotropic therapy ^v		X	X	X	X	X	X	X	X	X	X	X		
Mechanical ventilation and lung function ^w (start or stop date, FiO ₂ , PEEP, tidal volume, P/F ratio), ventilated patients only		X	X	X	X	X	X	X	X	X	X	X		
Adverse events	X	X	X											
Mortality	X	X	X											
Discharge from ICU or intermediate care unit / admission or discharge from hospital ^{Error! Reference source not found.}	X	X	X											

Abbreviations: AKI = acute kidney injury; ALT = alanine aminotransferase; APACHE = acute physiology and chronic health evaluation; APTT = activated partial thromboplastin time; AST = aspartate aminotransferase; BP = blood pressure; BUN = blood urea nitrogen; CPK = creatine phosphokinase; CRP = c-reactive protein; diff = differential; ECG = electrocardiogram; FiO₂ = fraction of inspired oxygen; GGT = gamma-glutamyl transpeptidase; GST-alpha = alpha-glutathione s-transferase; h = hour; Hct = hematocrit; Hgb = hemoglobin; HR = heart rate; ICU = intensive care unit; IgE = immunoglobulin E; IgG = immunoglobulin G; IL-6 = interleukin-6; IL-18 = interleukin-18; KIM-1 = kidney injury molecule-1; LBP = lipopolysaccharide binding protein; LDH = lactate dehydrogenase; OS = oxygen saturation; PEEP = positive end expiratory pressure; P/F ratio = fraction PaO₂/FiO₂; RR = respiratory rate; RRT = renal replacement therapy; SAPS-2 = simplified acute physiology score 2; SOFA = sequential organ failure assessment; T = temperature.

^v The AKI diagnosis can be made according to one of the AKIN serum creatinine criteria (absolute or relative increase, see inclusion criteria **Error! Reference source not found.** and **Error! Reference source not found.**), or according to the AKIN urine output criteria (urinary output < 0.5 mL/kg/h for > 6 hours, see inclusion criterion **Error! Reference source not found.**), the oliguria or anuria should still meet the AKIN urine output criteria prior to randomization and study drug administration.

^z Confirmatory.

- aa. Only for patients with liver disease.
- bb. Local laboratory.
- cc. See flowchart (Section **Error! Reference source not found.**, **Error! Reference source not found.**) for options and preference for reference serum creatinine value. The reference creatinine value is the serum creatinine value according to the following order of preference: 1) lowest value within 3 months of the hospital admission. If not available, 2) at hospital admission. If not available, 3) at ICU or intermediate care unit admission. If not available, 4) lowest value between 3 and 12 months prior to hospital admission.
- dd. When the diagnosis of AKI is made according to one of the AKIN serum creatinine criteria (absolute or relative increase, see inclusion criteria **Error! Reference source not found.** and **Error! Reference source not found.**), patients will be eligible for the study and can be randomly assigned when the volume-corrected serum creatinine sample, taken at screening confirms the continuation of AKI according to the AKIN criteria for serum creatinine. When the AKI diagnosis was made according to the AKIN urine output criteria (urinary output < 0.5 mL/kg/h for > 6 hours, see inclusion criterion **Error! Reference source not found.**), the oliguria or anuria should still meet the AKIN urine output criteria prior to randomization and study drug administration.
- ee. Vital signs in ambulant patients will be obtained with the patient in a sitting position and after 5 minutes rest. Blood pressure will be monitored non-invasively. In patients who already have an arterial line placed as part of standard or care, readings from invasive blood pressure monitoring are to be recorded.
- ff. Additionally, vital signs (excluding temperature) will also be monitored during study drug infusion on all treatment days at the following times: a) immediately before the administration of the study drug, b) within 5 minutes of the start of the study drug infusion, c) 30 minutes after the start of the study drug infusion, d) immediately after the completion of the administration of the study drug, which includes post-dose saline flushing, e) 30 and 60 minutes after completion of study drug administration, f) 2 hours, 3 hours, 4 hours, and 5 hours after completion of study drug administration (Day 1 only).
- gg. SOFA score to be obtained on each visit day as long as the patient is in the ICU or intermediate care unit, and at discharge from ICU or intermediate care unit .
- hh. EQ-5D will be performed at baseline, at discharge from the ICU or intermediate care unit, and at the Day 90 visit. In case the patient is unconscious, EQ-5D questionnaire will be completed by a next of kin.
 - ii. At 24 ± 1 hour after the previous drug administration.
- jj. Creatinine and BUN will be measured by a central laboratory. At Days 60 and 90, only serum creatinine will be measured. When patients have a Foley catheter, serum creatinine samples should be collected prior to and immediately after each urine collection for at least up to Day 7. If the patient is discharged from the ICU or intermediate care unit , the Foley catheter might be removed. In this case, a patient might urinate spontaneously and all efforts should be undertaken to start collecting urine produced from this time point onward. Approximately 6 hours later (exact duration needs to be recorded) the patient might urinate again and this urine will be used for analysis, and a blood sample will be drawn at this time too. The urine volume produced over approximately 6 hours will be entered in the eCRF.
 - kk. Urine creatinine and urea will be measured by a central laboratory. The central laboratory will calculate blood urea nitrogen (BUN) clearance at all visits from Day 1 to Day 7, inclusive, and on subsequent visit days if reliable urine collection is possible. Urine will be collected within a 6 ± 1 hour period at all visits from Day 1 to Day 28, only if reliable urine collection is possible (i.e., patient remains in the ICU or intermediate care unit or hospital).
- ll. These assessments will be performed before treatment if possible. Treatment should not be delayed because of these assessments.
- mmm. Urine volume collection in a 6 ± 1 hour collection period, only if reliable urine collection is possible (i.e., patient remains in the ICU or intermediate care unit or hospital). The volume should be corrected to account for the volume of samples previously taken from the total urine initially collected.
- nn. Only when possible within the 24-hour time window from first AKI diagnosis to treatment.
- oo. Assays will be performed by a central reference laboratory. See Section **Error! Reference source not found.** for sampling details.
- pp. A 12-lead ECG with at least 30-second rhythm strip will be recorded after the patient has rested supine or semi-recumbent for at least 5 minutes.
- qq. Central reference laboratory.
- rr. Samples taken on Days 60 and 90 will only be analyzed in case of a positive result on Day 28.

- ss. Verification that no concomitant medications that should be avoided are taken.
- tt. The actual stop date is collected for calculation of shock-free days. Only required when the patient is in the ICU or intermediate care unit.
- uu. Daily, as long as the patient requires mechanical ventilation. As appropriate, record start and stop dates and times of mechanical ventilation, including the settings required and the O₂ in the blood.
- vv. Actual admission dates and both planned and actual discharge dates from the ICU or intermediate care unit and hospital (planned meaning when decision is taken to discharge the patient, not necessarily being the same as the actual discharge date, e.g., because of lack of beds on the regular ward).

